18	SUSPENSION OR PREMATURE TERMINATION OF THE CLINICAL INVESTIGATION.....	35
19	VULNERABLE POPULATIONS.....	35
20	AMENDMENTS / MODIFICATIONS TO THE CLINICAL INVESTIGATION PLAN.....	35
21	PUBLICATION POLICY	36
22	REFERENCES	36
23	APPENDICES	37

1 Document History

Protocol Version Number	Date	Description of Changes	Change Author
1.0	27-DEC-2017	Initial Version	
2.0	23-FEB-2023	Sample size decreased to 50 End point changed from 5 years to 2 years Update to new protocol template format	[name]

Note:

Administrative Changes (Full CIRC review/approval not required) updates the Protocol Version to the next incremental decimal, e.g. 1.0 → 1.1

Substantive Changes (Full CIRC review/approval required) updates the Protocol Version to the next incremental integer, e.g. 1.0 → 2.0

2 Contact Information/List of Investigators

Title	A Longitudinal Outcomes Study of the Subchondroplasty® Procedure in the Hip
Protocol Number	CSU2017-03KC
Study Sponsor Contact Information	
[name] Clinical Research Specialist Zimmer Biomet [name] United States [contact] [contact]

Monitoring Contact Information	Zimmer Biomet or Designee
Name(s) and Address(es) of Principal Investigator(s) and Coordinating Investigator(s), as appointed (Clinical Investigation only as per Annex XV of EU MDR)	A complete listing and details including name, address, contact details and professional position of the Principal and Coordinating Investigators, as appointed, will be maintained in the Sponsor's Trial Master File.
Investigational Site Information (Clinical Investigation as per Annex XV of EU MDR)	The study will include up to 15 sites. Details regarding the site name(s) and address(es) will be maintained in the Sponsor's Trial Master File.
External Organizations, if applicable	N/A

3 Abbreviations

The following abbreviations are used throughout this study protocol.

ADE	Adverse Device Effect
AE	Adverse Event
CFR	Code of Federal Regulations
CRF	Case Report Form
CTA	Clinical Trial Agreement
DD	Device Deficiency
EC	Ethics Committee
eCRF	Electronic Case Report Form
EDC	Electronic Data Capture
EU MDR	European Regulation (EU) 2017/745
FDA	Food and Drug Administration
HIPAA	Health Insurance Portability and Accountability Act
ICF	Informed Consent Form
ICH	International Conference on Harmonisation (Harmonization)
IRB	Institutional Review Board
ISO	International Standards Organization
OR	Operating Room
PMCF	Post-Market Clinical Follow-Up
SAE	Serious Adverse Event
SADE	Serious Adverse Device Effect
UADE	Unanticipated Adverse Device Effect

4 Study Synopsis

Complete Protocol Title	A Longitudinal Outcomes Study of the Subchondroplasty® Procedure in the Hip
Protocol Number	CSU2017-03KC
Short Protocol Title	SCP Hip Outcomes Study
Sponsor	Zimmer Biomet, Warsaw, Indiana, United States
Manufacturer	Zimmer Biomet AccuFill® BSM ETEX Corporation [name] USA
Study Device(s)	AccuFill® Injectable Calcium Phosphate SCP® Surgical Instrumentation
Study Objectives/Endpoints	To collect data on the short- and long-term outcomes for subjects undergoing the Subchondroplasty® (SCP®) Procedure in the hip in a standard clinical setting. Outcomes to be assessed include medication usage, pain, function, activity levels and patient satisfaction.
Indications/Target Population	Candidates with at least one subchondral bone defect in the form of a cyst and/or bone marrow lesion (BML), insufficiency fracture or bone defect associated with early stage avascular osteonecrosis (AVN) in the femoral head, femoral neck and/or acetabulum who have elected to undergo or who have undergone the Subchondroplasty Procedure, will be enrolled in the study.
Inclusion/Exclusion Criteria	Candidates must meet ALL of the following: 
 1. Surgeon considers the patient appropriate for the SCP Procedure of the hip. 2. Subchondral bone defect(s) in the femoral head, femoral neck and/or acetabulum has been confirmed via radiographic finding on MRI or x-ray. 3. Subject provides voluntary signature on the IRB approved Informed Consent Form. 4. Subject is at least 18 years of age. 5. Subject must be physically and mentally willing and able, in the Investigator's opinion at the time of enrollment, to be compliant with the protocol and complete outcome forms via email, telephone, in-person or by regular mail.

	
Candidates will be excluded if they meet ANY of the following:
 
 1. Subject has collapse of subchondral bone. 2. Subject is pregnant at the time of surgery. 3. Subject is incarcerated. 4. Subject is involved in active litigation related to the condition being treated. 5. Subject is not comfortable with speaking, reading, and understanding questions and providing responses in an available language for the PROs in the protocol.
Study Design	This study is a post-market, single arm, non-randomized multi-center investigation.
Clinical Phase	Post-market
Sample Size	Approximately 50 study subjects implanted with the study device per cohort.
Length of Study	7 years (5 years of enrollment (all sites) and 2 years of follow-up)
Materials and Methods	Case report forms will be completed either in-office or hospital at Pre-op, Surgery, Discharge, and 6 weeks, 1-year, and 2-years.
Data Collection	Paper/Electronic
Statistical Reporting	Data collected will be summarized and reported to each participating investigator. Statistical analysis will be conducted by Zimmer Biomet or its designee.
Scores/Performance Assessments	
Pre-Operative
 
Initial study procedures include patient demographics, medical history and hip history. Additionally, the following measures will be obtained pre-operatively:
 
 • Use of pain medication and therapy • Subject-reported outcomes: 
 ○ Numeric Pain Scale ○ Modified Harris Hip Score ○ Hip Outcome Score ○ EQ-5D 
Subjects will complete only the Numeric Pain Scale at 2 weeks post-operatively.

	
Post-Operative
 
Thereafter, subjects complete self-reported outcomes measures post-operatively at 6 weeks, 12 weeks, 6 months, 1 year and 2 years. These measures include:
 
 • Use of pain medication and therapy • Subject-reported outcomes: 
 ○ Numeric Pain Scale ○ Modified Harris Hip Score ○ Hip Outcome Score ○ EQ-5D ○ Subject Global Satisfaction Survey 
The post-operative visit data must be collected for each enrolled subject via email, telephone, in-person or by regular mail. If the subject is not seen in person, a member of the study staff will contact the subject by telephone at the above time points to inquire about their outcomes, any conversion surgeries, and/or adverse events.

Standards	
The PMCF is compliant with the below:
 
 • ISO 14155: 2020 - Clinical investigation of medical devices for human subjects - Good clinical practice. • The Declaration of Helsinki (DoH) - Ethical principles for medical research involving human subjects. • European Regulation (EU) 2017/745
Study Funding	
Funding for this clinical study is made available by Zimmer Biomet to support clinical data collection, IRB/EC review fees and other expenses associated with the conduct and execution of this study protocol as outlined in the fully executed Clinical Trial Agreement.

5 Data Collection Overview

Table 1 - Schedule of Events						
	Enrollment		Follow-Up			
Event/Visit	Pre-Operative	Surgery	2 Weeks	6 Weeks	12 Weeks 6 Months	1 Year 2 Years
Visit Window	≤60 Days Prior to Surgery		±7 Days	±7 Days	±14 Days	±60 Days
Informed Consent	X					
CRF 1: Inclusion & Exclusion Criteria	X					
CRF 2: Subject History	X					
CRF 3: Numeric Pain Scale	P		P	P	P	P
CRF 4: Pain Medication & Therapy	X			P	P	P
CRF 5: Modified Harris Hip Score	P			P	P	P
CRF 6: Hip Outcome Score	P			P	P	P
CRF 7: EQ-5D	P			P	P	P
CRF 8: Subject Global Satisfaction Survey				P	P	P
CRF 9: Operative Details		X				
CRF 10: End of Study/Withdrawal ¹		(X)	(X)	(X)	(X)	(X)
CRF 11: Adverse Event ²		(X)	(X)	(X)	(X)	(X)
CRF 12: Protocol Violation ²	X	X	X	X	X	X

X Investigator or designated staff completed forms

¹ End of Study/Withdrawal form will be completed if the subject is no longer participating in the study for any reason.

(X) Investigator completed forms, if applicable

² Case Report Form to be completed if/when event occurs.

P Subject completed form

6 Introduction and Purpose

6.1 Clinical Background

Subchondral bone defects are MRI-visible defects that can be seen on fat-suppressed MRI sequences (T2FS, PDFS, etc.) where they appear as a hazy white area against the background of darker bone [1].

Subchondral bone defects are frequently associated with pain [2], cartilage defects, cartilage volume loss [3] and increased odds of progression to joint replacement [2]. Similarly, subchondral bone defects of the hip are associated with hip pain and hip joint space narrowing [4] that typically resolves spontaneously in approximately 6 to 9 months [5]. Treatment usually consists of avoiding load on the hips as well as the use of nonsteroidal anti-inflammatory drugs (NSAID), bisphosphonates, and prostacyclin, which can improve local hemodynamic characteristics [6, 7]. Unfortunately, in some cases, conservative treatment approaches do not relieve symptoms. In these cases, the disease becomes prolonged and intractable, causing a great deal of discomfort. Various treatments have been proposed in an attempt to shorten the natural course of the disease, which is frequently associated with severe and long-lasting disability [6].

In general, the therapeutic approach to subchondral bone defects of the hip is based on its suspected etiology and ranges from various symptomatic therapies [6, 7] to more invasive treatments, such as core decompression or even Total Hip Arthroplasty (THA) [8]. Because it is considered a fully reversible disease [6], there is controversy regarding whether treatment should be conservative or invasive. Total Hip Arthroplasty is an invasive treatment and can result in complications, including bleeding, wound complication, thromboembolic disease, neural deficit, vascular injury, dislocation/instability, periprosthetic fracture, abductor muscle disruption, deep periprosthetic joint infection, heterotopic ossification, bearing surface wear, osteolysis, implant loosening, cup-liner dissociation, implant fracture, reoperation, revision, readmission, and death [9]. Therefore, there is a need for an effective less invasive treatment.

Subchondroplasty® (SCP®) is a minimally-invasive procedure first described in 2007 to fill subchondral osseous defects associated with subchondral bone defects using an injectable bone substitute material (BSM), AccuFill® [10]. AccuFill has unique properties that allow it to flow through the osseous defects in trabecular bone and then set up hard at body temperature [11]. Two year results from a clinical study of the knee on 66 subjects considering total knee arthroplasty (TKA) has shown improvements in subject reported pain and function with only 30% of subjects undergoing revision to TKA at 2 years [12]. The goal of this study is to track outcomes in a population undergoing SCP of the hip.

6.2 Preclinical Studies

Preclinical studies in established animal models were used to evaluate safety and effectiveness of AccuFill for treatment of a critical sized bone defect. A rabbit bilateral lateral femoral condyle defect model (4.8 mm diameter x 6 mm length cylindrical defect) through 24

weeks demonstrated that AccuFill caused bone induction and osteointegration at the implant site, and was well tolerated.

No significant adverse events or indications of infections or rejections of the AccuFill material were observed in the preclinical evaluations of AccuFill. Studies demonstrated bone induction, osteointegration and potential for use as bone void filler.

6.3 Regulatory Overview of Subchondroplasty

This study will evaluate the on-label use of AccuFill during the Subchondroplasty Procedure.

The Subchondroplasty Procedure will be performed using two commercially available devices. The regulatory status of each component of the system is described below:

1. AccuFill® Injectable Calcium Phosphate – Class II device; 510(k) Number K093447 - Calcium Salt Bone Void Filler Device, cleared by FDA. The package insert provides product description, indications, and usage information.
2. SCP® Surgical Instrumentation – These are Class I manual surgical instruments. Per 21 CFR 888.4540 and 21 CFR 878.4800, these manual surgical instruments are premarket exempt.

6.4 Risk Analysis

This study was designed to assure that the benefits and knowledge gained by studying clinical outcomes associated with Subchondroplasty for treatment of subchondral bone defects in the hip outweigh the potential risks to the subjects. Alternative treatment options may require more invasive surgical therapy to treat the hip pain, up to and including Total Hip Arthroplasty (THA).

6.4.1 Risks of Surgical Intervention

Risks of surgical intervention include those risks currently associated with arthroscopic surgical interventions in the hip. These risks include intra-articular adhesions (scar tissue), superficial and/or deep wound infection, nausea and/or vomiting, bleeding, hip pain, muscle weakness, and postoperative blood clot (hematoma). There are possibilities of wound re-opening, deep vein thrombosis (blood clot), pulmonary embolus (lung clot), vascular or nerve injury and an allergic response to the anesthetic or medications. Some additional risks related to local anesthesia are swelling, pain, bleeding, bruising, nerve pain and loss of sensation in the skin and ligament around the hip.

6.4.2 Risks Associated with Subchondral Implantation of AccuFill

Risks specific to the implantation of a bone substitute material may include tissue thinning over the implant site, tenderness/redness/edema, seroma/hematoma, infection, swelling/fluid collection, loss of contour. Additionally, material extravasation may occur in the joint. In the event of this occurrence, any extravasation of material into surrounding soft tissues should be thoroughly irrigated at the time of the procedure. If not initially planned, arthroscopy or mini-open approach to the hip may

be necessary to remove extravasated material. Migration, extrusion, dehiscence, fracture and sloughing of AccuFill can occur as a result of excessive trauma. Neurovascular injury may occur due to surgical trauma. A pulmonary embolism may result from using this injectable bone void filler.

6.4.3 Methods to Minimize Risk

Only appropriate subjects, who meet the inclusion and exclusion criteria, will be recruited into the study. Study subjects will be monitored post-operatively to assess the surgical site for any acute and chronic adverse reactions to ensure proper medical treatment can be administered. Validated and standardized outcome scales and surveys will be used to collect subjects' data. Experienced orthopedic surgeons will participate as Investigators and have experienced staff to perform the study procedures.

6.4.4 Benefits and Justification for the Study

This is an observational study and there are no direct benefits to the subject, other than those associated with the treatment of a subchondral bone defect of the hip. The justification for this study is to learn more about patient outcomes following the Subchondroplasty procedure in the hip.

7 Study Device Information

7.1 Study Device

The Subchondroplasty Procedure targets and fills subchondral bone defects in the form of a cyst and/or bone marrow lesion (BML), insufficiency fracture or bone defect associated with early stage avascular osteonecrosis (AVN) with AccuFill BSM utilizing an arthroscopic / percutaneous approach as follows. Preoperatively, the subchondral bone defect is identified on a fat-suppressed MRI, and the approach and trajectory is planned based on defect location. Using intraoperative fluoroscopy, the bone defect is localized relative to MRI findings. The appropriate AccuPort® Delivery Cannula is drilled to the bone defect. AccuFill BSM is then injected into the subchondral bone defect. The AccuFill fills the defect and hardens within the subchondral bone defect, and is resorbed over time and replaced with new bone during the healing process.

It is recommended that a hip arthroscopy be performed prior to or after the Subchondroplasty procedure. In either case, the arthroscope should be placed into the joint after injection of AccuFill to check for possible material extravasation. Using standard arthroscopic surgery techniques, skin incisions are made for the insertion of arthroscopic instrumentation.

7.2 Instrumentation

The SCP® Surgical Instrumentation is a set of manual surgical instruments used to target and

deliver AccuFill® to the osseous defect.

7.3 Compatibility

To determine whether devices have been authorized for use in a proposed combination with Zimmer and/or Biomet products, please contact your sales representative or visit the Zimmer Electronic Labeling Service (eLabeling) website: <https://labeling.zimmerbiomet.com/>

8 Study Population

Approximately 50 subjects, each with at least one subchondral bone defect in the form of a cyst and/or bone marrow lesion (BML), insufficiency fracture or bone defect associated with early stage avascular osteonecrosis (AVN) in the femoral head, femoral neck and/or acetabulum who have elected to undergo or who have undergone the Subchondroplasty Procedure, will be enrolled in the study.

8.1 Inclusion Criteria

Candidates must meet ALL of the following:

Surgeon considers the patient appropriate for the SCP Procedure of the hip.

Subchondral bone defect(s) in the femoral head, femoral neck and/or acetabulum has been confirmed via radiographic finding on MRI or x-ray.

Subject provides voluntary signature on the IRB approved Informed Consent Form.

Subject is at least 18 years of age.

Subject must be physically and mentally willing and able, in the Investigator's opinion at the time of enrollment, to be compliant with the protocol and complete outcome forms via email, telephone, in-person or by regular mail.

8.2 Exclusion Criteria

Candidates will be excluded if they meet ANY of the following:

Subject has collapse of subchondral bone.

Subject is pregnant at the time of surgery.

Subject is incarcerated.

Subject is involved in active litigation related to the condition being treated.

Subject is not comfortable with speaking, reading, and understanding questions and providing responses in an available language for the PROs in the protocol.

9 Study Objectives

The purpose of this post-market clinical study is to collect short- and long-term outcomes for subjects undergoing the Subchondroplasty Procedure in the hip in a standard clinical setting. Outcomes to be assessed include medication usage, pain, function, activity levels and patient

satisfaction.

10 Study Design and Endpoints

10.1 Disease/Condition Being Treated

Subchondral bone defects in the form of a cyst and/or bone marrow lesion (BML), insufficiency fracture or bone defect associated with early stage avascular osteonecrosis (AVN) in the femoral head, femoral neck and/or acetabulum.

10.2 Number of Sites and Regions

Up to 15 sites in the United States

10.3 Number of Cases and Maximum Enrollment per Investigation Site

A total number of approximately 50 subjects across 15 sites in the United States.

10.4 Study Design

This study is designed as a post-market, single arm, non-randomized multi-center investigation.

Male and female subjects, at least 18 years of age, with at least one subchondral bone defect in the form of a cyst and/or bone marrow lesion (BML), insufficiency fracture or bone defect associated with early stage avascular osteonecrosis (AVN) in the femoral head, femoral neck and/or acetabulum who are suitable candidates for use of AccuFill during the Subchondroplasty Procedure are eligible for enrollment in this study.

A maximum of 15 study sites, in the United States of America, will enroll a target of 50 subjects.

Each Investigator must obtain IRB approval, or favorable opinion by an EC, prior to consent of the first subject; no study-related procedures can occur without the approval and oversight of a registered IRB or EC. If the study site does not have an IRB of record, a central IRB may be utilized upon approval by Zimmer Biomet.

Demographics, medical history, hip history and use of pain medication and therapy will be recorded at the time of subject consent. Additionally, patient reported outcomes measures will be obtained pre-operatively. Operative details including the SCP Procedure, concomitant surgical procedures and intraoperative safety events will be recorded at the time of surgery. Prospective subjects will be considered enrolled in this study once their Subchondroplasty Procedure has been performed.

Subjects will complete only the Numeric Pain Scale at 2 weeks post-operatively. Thereafter, subjects will complete self-reported outcomes measures post-operatively at 6 weeks, 12 weeks, 6 months, 1 year and 2 years. These measures include information on pain medication and therapy, pain levels, function, activity and subject satisfaction. Screening for adverse events and conversion will occur throughout the study.

Subjects will complete the study at 2 years or will be withdrawn if they undergo conversion of the Subchondroplasty site. For the purposes of this protocol, a conversion will be defined as

total hip arthroplasty or any procedure involving removal of the AccuFill material on the index hip.

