10.7.1 Primary Endpoint

The primary endpoint is defined by the overall group mean improvement from baseline of the Modified Harris Hip Score at the two year time point. The safety of the system will be assessed by monitoring the frequency and incidence of adverse events. Relation of the events to implant (Accufill®), instrumentation (SCP® Surgical Instrumentation) and/or procedure should be specified.

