11.9 Surgical Reoperation or Revision

A reoperation of the index hip or revision of the SCP injection site may be performed at the discretion of the Investigator (e.g., due to progressive pain or disability, etc.). A reoperation is defined as any surgical procedure on the index hip. For the purposes of this protocol, a revision will be defined as any partial or total joint arthroplasty or any fusion, bone fixation, bone grafting, or bone substitute procedure in the study hip.

If the reoperation occurs due to an adverse event, the event should be documented on a Serious Adverse Event Form and an Exit Form completed, and the subject exited from the study.

In the event that a revision occurs (defined as any partial or total joint arthroplasty or any fusion, bone fixation, bone grafting, or bone substitute procedure in the index hip), the subject will be exited from the study. A Serious Adverse Event Form and an Exit Form will be completed.

Use of any postoperative injections into the index hip should be recorded on the Medication Form at the next questionnaire completion window.

12 Reporting

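### Subjects are exited at conversion, revision or AE-driven reoperation with no rule for including them, so the two-year primary mean covers only the remaining hips and overstates the result if those events count as failure

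*Combined protocol and SAP*

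**What the plan says.** Section 10.7.1 sets the primary endpoint as the "overall group mean improvement from baseline of the Modified Harris Hip Score at the two year time point".

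Several sections end participation before that time point:

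- Section 10.4: "Subjects will complete the study at 2 years or will be withdrawn if they undergo conversion of the Subchondroplasty site". Conversion is "total hip arthroplasty or any procedure involving removal of the AccuFill material on the index hip".
- Section 11.9, revision: after any arthroplasty, fusion, fixation, grafting or "bone substitute procedure in the index hip), the subject will be exited from the study".
- Section 11.9, reoperation caused by an adverse event: a Serious Adverse Event Form, "an Exit Form completed, and the subject exited from the study".
- Section 12.4.2 requires an exit form once a revision is done.
- Section 12.4.8 ends participation at a revision that removes a study device.

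Section 12.4.4 keeps data gathered before withdrawal and provides for none afterwards. It also words conversion more narrowly than 10.4 (total removal of AccuFill rather than any removal) and makes discontinuation permissive.

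Sections 16.2 and 16.3 plan descriptive summaries with 95% confidence intervals. They name no analysis set, no treatment of missing two-year scores, no value for a converted or revised hip, no time-to-event summary and no sensitivity analysis. Section 16.1 allows for 25% attrition only by raising 24 subjects to 32.

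The only failure rate in the document is in Section 6.1 and concerns the knee: "with only 30% of subjects undergoing revision to TKA at 2 years".

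**The concern.** Leaving the study in this way is not a neutral loss. Section 11.9 itself gives worsening pain or disability as an example of why a hip would be reoperated or revised, so exit is triggered by the outcome that the primary score measures. Recruiting a consecutive series (Sections 10.5 and 10.6) guards against selection at entry, and the exit rule then brings selection back at the end.

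The endpoint is described as an overall group result, yet it would be read from a subset that becomes more favourable as more hips are reoperated and leave. With a single arm there is no comparator that would reveal this. Adverse-event collection also stops in the same subjects, although safety is part of the same endpoint section. Enrolling more subjects than needed protects precision but does nothing about selection.

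**Working it through.** **Inputs.** From Section 16.1: mean improvement 31.4, SD 22.4, threshold (MCID) 18.0, power 80%, alpha 0.05, attrition 25%. From Section 10.3: about 50 subjects. From Section 6.1: 30%, the knee rate. Assumed, because the documents do not give them: the share *f* of subjects exited for these events, and the change *m* credited to an exited hip.

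**The plan's own figure.** The planning margin is 31.4 − 18.0 = 13.4. A two-sided one-sample t-test at 0.05 with SD 22.4 has power 78.3% at n = 23 and 80.1% at n = 24. Then 24 / (1 − 0.25) = 32. Both stated numbers reproduce, so the sample-size arithmetic is not at fault.

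**Effect on the mean.** Suppose retained hips improve by 31.4 on average.

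- Mean over all subjects = (1 − f) × 31.4 + f × m
- Overstatement = 31.4 − that mean = f × (31.4 − m)

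With m = 0 this is 0.314 points for each 1% of subjects exited.

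**Effect on power, all 50 analysed against 18.0.** Two variance assumptions bracket the result for m = 0:

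- (a) every exited hip is set to exactly 0: SD = √[(1 − f) × 22.4² + f(1 − f) × 31.4²]
- (b) exited hips vary around 0 with SD 22.4: SD = √[22.4² + f(1 − f) × 31.4²]

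| f | Mean over all subjects | Overstatement | Share of 13.4 | SD (a) / (b) | Power (a) / (b) |
|---|---|---|---|---|---|
| 10% | 28.3 | 3.1 | 23% | 23.2 / 24.3 | 86% / 83% |
| 20% | 25.1 | 6.3 | 47% | 23.6 / 25.7 | 55% / 48% |
| 30% | 22.0 | 9.4 | 70% | 23.6 / 26.6 | 21% / 18% |

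The mean over all subjects falls to 18.0 when f = 1 − 18.0/31.4 = 42.7%.

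**Sensitivity to the credited value, at f = 30%.** With m = +10 the mean is 25.0 and the overstatement 6.4. With m = −10 they are 19.0 and 12.4.

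**For contrast.** Under the exit rule as written, the mean among retained hips stays at 31.4 whatever f is. With 35 retained hips (30% of 50 exited, no other loss) the power against 18.0 is still 93%. The observed analysis therefore barely registers the failures.

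**The case against.** Four objections have weight.

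*Direction.* A reader might infer that the primary mean is biased upward without qualification. The documents do not support that, because they define no target of estimation. If the target were the score regardless of later surgery, hips that went on to arthroplasty might score well or badly at two years, and the direction could not be determined. The upward direction holds when conversion, revision or AE-driven reoperation counts as failure of the procedure. Nor does the mean cover only hips that did well, since hips doing poorly without further surgery stay in it.

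*Analysis set.* The plan nowhere states that only completers are analysed. This stands as a matter of wording, but exited subjects have no two-year score and nothing is substituted, so no other two-year mean can be computed from what is specified.

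*Size.* A reader might take 30% as the expected hip rate. It comes from knee subjects who were already considering knee replacement. This study excludes subchondral collapse (Section 8.2), Section 6.1 describes hip lesions as usually resolving spontaneously, and 30% exceeds the plan's total attrition of 25%. The 31.4 and 22.4 are one-year Harris Hip Score inputs, and Section 16.1 does not say whether failures were excluded from them. The 10% case deserves equal prominence.

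*False success.* One can compute how often a 95% interval would lie above 18.0 when the true all-subject mean is exactly 18.0 and exited hips are credited with 0. The retained mean is then 18/(1 − f) with 45, 40 or 35 hips, giving about 8.5%, 24% and 51% at 10%, 20% and 30%, against a nominal 2.5%. Calling this an error rate presumes a decision rule, and Section 16.3 lists intervals without a test or success criterion.

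Failures are also not hidden: conversion is screened for throughout, each revision needs a Serious Adverse Event Form, and complications are tabulated. That lets a reader see the losses but does not repair the mean.

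**Conclusion.** The point holds in a conditional form. The exit rules remove subjects from the two-year score because of an event tied to the outcome, and Section 16 has no rule that brings them back. The mean described as the overall group result is in fact a mean over hips not converted, revised or reoperated for an adverse event. It overstates the result of the procedure if those events count as failure.

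The mechanism is certain from the text; the size is not. The range of 3.1 to 9.4 points rests on an exit share of 10% to 30%, a credit of 0 for exited hips, and one-year Harris Hip Score inputs carried to a two-year Modified Harris Hip Score. On the same assumptions, the claim in Section 16.1 that 50 subjects give more than adequate power survives at 10% exit but not at 20% or 30%.

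**What to change.** 1. In Sections 10.4, 11.9, 12.4.2, 12.4.4 and 12.4.8, reconcile the differing definitions of conversion, revision and reoperation, since they decide which hips leave the mean. Separate these events from study exit, so that remote questionnaires and adverse-event collection continue to two years.
2. In Sections 10.7.1 and 16.3, define the primary mean over all implanted subjects with a baseline score. Give one stated failure value (for example, change = 0) to every subject with a reconciled failure event, and say explicitly whether AE-driven reoperation is such an event. Report two sensitivity analyses: the mean among hips without an event, and the mean using the scores collected after the event.
3. Report the number and cumulative incidence of these events, with a 95% confidence interval, beside the mean.
4. For two-year scores missing for other reasons, use a mixed model on the 6-week, 12-week, 6-month and one-year scores already scheduled.
5. Restate the power in Section 16.1 for this definition over a range of event rates.

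The cost is protocol and analysis wording and a few extra questionnaires, which can be collected remotely because Section 11.7 already does not require office visits. No extra patients are called for by the change itself. The downside is a less favourable headline mean and a lower stated power.
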